10.9 Use In Nursing Women

It is unknown whether pembrolizumab is excreted in human milk. Since many drugs are excreted in human milk, and because of the potential for serious adverse reactions in the nursing infant, subjects who are breast-feeding are not eligible for enrollment.

11 PHARMACEUTICAL INFORMATION

11.1 Pembrolizumab (MK-3475)

11.1.1 Source

Pembrolizumab will be provided to the NCI pharmacy as part of a clinical trial agreement.

There will be no IND obtained for the use of Pembrolizumab in this study. This study meets the criteria for exemption for an IND as this investigation is not intended to support a new indication for use or any other significant change to the labeling; the drug is already approved and marketed and the investigation is not intended to support a significant change in advertising; and the investigation does not involve a route of administration or dosage level in use in a patient population or other factor that significantly increases the risks (or decreases the acceptability of the risks) associated with the use of the drug product.

11.1.2 Toxicity

- Immune-mediated pneumonitis, including fatal cases, occurred in patients receiving pembrolizumab. Pneumonitis occurred in 32 (2.0%) of 1567 patients, including Grade 1 (0.8%), 2 (0.8%), and 3 (0.4%) pneumonitis. Monitor patients for signs and symptoms of pneumonitis. Evaluate suspected pneumonitis with radiographic imaging. Administer corticosteroids for Grade 2 or greater pneumonitis. Withhold pembrolizumab for Grade 2; permanently discontinue pembrolizumab for Grade 3 or 4 or recurrent Grade 2 pneumonitis.
- Immune-mediated colitis occurred in 31 (2%) of 1567 patients, including Grade 2 (0.5%), 3 (1.1%), and 4 (0.1%) colitis. Monitor patients for signs and symptoms of colitis. Administer corticosteroids for Grade 2 or greater colitis. Withhold pembrolizumab for Grade 2 or 3; permanently discontinue pembrolizumab for Grade 4 colitis.
- Immune-mediated hepatitis occurred in 16 (1%) of 1567 patients, including Grade 2 (0.1%), 3 (0.7%), and 4 (0.1%) hepatitis. Monitor patients for changes in liver function. Administer corticosteroids for Grade 2 or greater hepatitis and, based on severity of liver enzyme elevations, withhold or discontinue pembrolizumab.
- Hypophysitis occurred in 13 (0.8%) of 1567 patients, including Grade 2 (0.3%), 3 (0.3%), and 4 (0.1%) hypophysitis. Monitor patients for signs and symptoms of hypophysitis (including hypopituitarism and adrenal insufficiency). Administer corticosteroids and hormone replacement as clinically indicated. Withhold pembrolizumab for Grade 2; withhold or discontinue for Grade 3 or 4 hypophysitis.
- Hyperthyroidism occurred in 51 (3.3%) of 1567 patients, including Grade 2 (0.6%) and 3 (0.1%) hyperthyroidism. Hypothyroidism occurred in 127 (8.1%) of 1567 patients, including Grade 3 (0.1%) hypothyroidism. Thyroid disorders can occur at any time during treatment. Monitor patients for changes in thyroid function (at the start of treatment, periodically during treatment, and as indicated based on clinical evaluation) and for clinical signs and symptoms of thyroid disorders. Administer replacement hormones for hypothyroidism and manage hyperthyroidism with thionamides and beta-blockers as appropriate. Withhold or discontinue pembrolizumab[®] (pembrolizumab) for Grade 3 or 4 hyperthyroidism.
- Type 1 diabetes mellitus, including diabetic ketoacidosis, occurred in 3 (0.1%) of 2117 patients. Monitor patients for hyperglycemia or other signs and symptoms of diabetes. Administer insulin for type 1 diabetes, and withhold pembrolizumab and administer anti-hyperglycemics in patients with severe hyperglycemia.
- Immune-mediated nephritis occurred in 7 (0.4%) of 1567 patients, including Grade 2 (0.2%), 3 (0.2%), and 4 (0.1%) nephritis. Monitor patients for changes in renal function. Administer corticosteroids for Grade 2 or greater nephritis. Withhold pembrolizumab for Grade 2; permanently discontinue pembrolizumab for Grade 3 or 4 nephritis.
- Other clinically important immune-mediated adverse reactions can occur. For suspected immune-mediated adverse reactions, ensure adequate evaluation to confirm etiology or exclude other causes. Based on the severity of the adverse reaction, withhold

pembrolizumab and administer corticosteroids. Upon improvement to Grade 1 or less, initiate corticosteroid taper and continue to taper over at least 1 month. Based on limited data from clinical studies in patients whose immune-related adverse reactions could not be controlled with corticosteroid use, administration of other systemic immunosuppressants can be considered. Resume pembrolizumab when the adverse reaction remains at Grade 1 or less following corticosteroid taper. Permanently discontinue pembrolizumab for any Grade 3 immune-mediated adverse reaction that recurs and for any life-threatening immune-mediated adverse reaction.

- The following clinically significant, immune-mediated adverse reactions occurred in less than 1% (unless otherwise indicated) of 1567 patients: arthritis (1.6%), exfoliative dermatitis, bullous pemphigoid, uveitis, myositis, Guillain-Barré syndrome, myasthenia gravis, vasculitis, pancreatitis, hemolytic anemia, and partial seizures arising in a patient with inflammatory foci in brain parenchyma.
- Severe and life-threatening infusion-related reactions have been reported in 3 (0.1%) of 2117 patients. Monitor patients for signs and symptoms of infusion-related reactions including rigors, chills, wheezing, pruritus, flushing, rash, hypotension, hypoxemia, and fever. For Grade 3 or 4 reactions, stop infusion and permanently discontinue pembrolizumab.
- Based on its mechanism of action, pembrolizumab can cause fetal harm when administered to a pregnant woman. If used during pregnancy, or if the patient becomes pregnant during treatment, apprise the patient of the potential hazard to a fetus. Advise females of reproductive potential to use highly effective contraception during treatment and for 4 months after the last dose of pembrolizumab.
- In Trial 6, pembrolizumab was discontinued due to adverse reactions in 9% of 555 patients; adverse reactions leading to discontinuation in more than one patient were colitis (1.4%), autoimmune hepatitis (0.7%), allergic reaction (0.4%), polyneuropathy (0.4%), and cardiac failure (0.4%). Adverse reactions leading to interruption of pembrolizumab occurred in 21% of patients; the most common ($\geq 1\%$) was diarrhea (2.5%). The most common adverse reactions with pembrolizumab vs ipilimumab were fatigue (28% vs 28%), diarrhea (26% with pembrolizumab), rash (24% vs 23%), and nausea (21% with pembrolizumab). Corresponding incidence rates are listed for ipilimumab only for those adverse reactions that occurred at the same or lower rate than with pembrolizumab.
- In Trial 2, pembrolizumab was discontinued due to adverse reactions in 12% of 357 patients; the most common ($\geq 1\%$) were general physical health deterioration (1%), asthenia (1%), dyspnea (1%), pneumonitis (1%), and generalized edema (1%). Adverse reactions leading to interruption of pembrolizumab occurred in 14% of patients; the most common ($\geq 1\%$) were dyspnea (1%), diarrhea (1%), and maculo-papular rash (1%). The most common adverse reactions with pembrolizumab vs chemotherapy were fatigue (43% with pembrolizumab), pruritus (28% vs 8%), rash (24% vs 8%), constipation (22% vs 20%), nausea (22% with pembrolizumab), diarrhea (20% vs 20%), and decreased appetite (20% with pembrolizumab). Corresponding incidence rates are listed for

chemotherapy only for those adverse reactions that occurred at the same or lower rate than with pembrolizumab.

- No formal pharmacokinetic drug interaction studies have been conducted with pembrolizumab.
- It is not known whether pembrolizumab is excreted in human milk. Because many drugs are excreted in human milk, instruct women to discontinue nursing during treatment with pembrolizumab and for 4 months after the final dose.
- Safety and effectiveness of pembrolizumab have not been established in pediatric patients.

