3.3.1 Dose Modifications

Adverse events (both non-serious and serious) associated with pembrolizumab exposure may represent an immunologic etiology. These adverse events may occur shortly after the first dose or several months after the last dose of treatment. Pembrolizumab must be withheld for drug-related toxicities and severe or life-threatening AEs as per **Table 4** below. See Section 4 for supportive care guidelines, including use of corticosteroids.

Table 4. Dose Modification Guidelines for Drug-Related Adverse Events

Toxicity	Hold Treatment For Grade	Timing for Restarting Treatment	Treatment Discontinuation
Diarrhea/Colitis	2-3	Toxicity resolves to Grade 0-1	Toxicity does not resolve within 12 weeks of last dose or inability to reduce corticosteroid to 10 mg or less of prednisone or equivalent per day within 12 weeks
	4	Permanently discontinue	Permanently discontinue
AST, ALT, or Increased Bilirubin	2	Toxicity resolves to Grade 0-1	Toxicity does not resolve within 12 weeks of last dose
	3-4	Permanently discontinue (see exception below) ^a	Permanently discontinue
Type 1 diabetes mellitus (if new onset) or Hyperglycemia	T1DM or 3-4	Hold pembrolizumab for new onset Type 1 diabetes mellitus or Grade 3-4 hyperglycemia associated with evidence of beta cell failure	Resume pembrolizumab when patients are clinically and metabolically stable
Hypophysitis	2-4	Toxicity resolves to Grade 0-1. Therapy with pembrolizumab can be continued while endocrine replacement therapy is instituted	Toxicity does not resolve within 12 weeks of last dose or inability to reduce corticosteroid to 10 mg or less of prednisone or equivalent per day within 12 weeks

Toxicity	Hold Treatment For Grade	Timing for Restarting Treatment	Treatment Discontinuation
Hyperthyroidism	3	Toxicity resolves to Grade 0-1	Toxicity does not resolve within 12 weeks of last dose or inability to reduce corticosteroid to 10 mg or less of prednisone or equivalent per day within 12 weeks
	4	Permanently discontinue	Permanently discontinue
Hypothyroidism		Therapy with pembrolizumab can be continued while thyroid replacement therapy is instituted	Therapy with pembrolizumab can be continued while thyroid replacement therapy is instituted
Infusion Reaction	2 ^b	Toxicity resolves to Grade 0-1	Permanently discontinue if toxicity develops despite adequate premedication
	3-4	Permanently discontinue	Permanently discontinue

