Pneumonitis	2	Toxicity resolves to Grade 0-1	Toxicity does not resolve within 12 weeks of last dose or inability to reduce corticosteroid to 10 mg or less of prednisone or equivalent per day within 12 weeks
	3-4	Permanently discontinue	Permanently discontinue
Renal Failure or Nephritis	2	Toxicity resolves to Grade 0-1	Toxicity does not resolve within 12 weeks of last dose or inability to reduce corticosteroid to 10 mg or less of prednisone or equivalent per day within 12 weeks
	3-4	Permanently discontinue	Permanently discontinue
All Other Drug-Related Toxicity ^c	3 or Severe	Toxicity resolves to Grade 0-1	Toxicity does not resolve within 12 weeks of last dose or inability to reduce corticosteroid to 10 mg or less of prednisone or equivalent per day within 12 weeks
	4	Permanently discontinue	Permanently discontinue

Note: Permanently discontinue for any severe or Grade 3 drug-related AE that recurs or any life-threatening event.

^a For patients with liver metastasis who begin treatment with Grade 2 AST or ALT, if AST or ALT increases by greater than or equal to 50% relative to baseline and lasts for at least 1 week then patients should be discontinued.

^b If symptoms resolve within one hour of stopping drug infusion, the infusion may be restarted at 50% of the original infusion rate (e.g., from 100 mL/hr to 50 mL/hr). Otherwise dosing will be held until symptoms resolve and the subject should be premedicated for the next scheduled dose; Refer to **Table 5** – Infusion Reaction Treatment Guidelines for further management details.

^c Patients with intolerable or persistent Grade 2 drug-related AE may hold study medication at physician discretion. Permanently discontinue study drug for persistent Grade 2 adverse reactions for which treatment with study drug has been held, that do not recover to Grade 0-1 within 12 weeks of the last dose.

Dosing interruptions are permitted in the case of medical / surgical events or logistical reasons not related to study therapy (e.g., elective surgery, unrelated medical events, patient vacation, and/or holidays). Subjects should be placed back on study therapy within 6 weeks of the

Abbreviated Title: Pembrolizumab in MTC

Version Date: 3/26/18

scheduled interruption. The reason for interruption should be documented in the patient's study record.

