4.1.3 Supportive Care Guidelines

Subjects should receive appropriate supportive care measures as deemed necessary by the treating investigator. Suggested supportive care measures for the management of adverse events with potential immunologic etiology are outlined below. Where appropriate, these guidelines include the use of oral or intravenous treatment with corticosteroids as well as additional anti-inflammatory agents if symptoms do not improve with administration of corticosteroids. Note that several courses of steroid tapering may be necessary as symptoms may worsen when the steroid dose is decreased. For each disorder, attempts should be made to rule out other causes such as metastatic disease or bacterial or viral infection, which might require additional supportive care. The treatment guidelines are intended to be applied when the investigator determines the events to be related to pembrolizumab.

Note: if after the evaluation the event is determined not to be related, the investigator does not need to follow the treatment guidance (as outlined below). Refer to Section **3.3.1** for dose modification.

It may be necessary to perform conditional procedures such as bronchoscopy, endoscopy, or skin photography as part of evaluation of the event.

- **Pneumonitis:**
 - For **Grade 2 events**, treat with systemic corticosteroids. When symptoms improve to Grade 1 or less, steroid taper should be started and continued over no less than 4 weeks.
 - For **Grade 3-4 events**, immediately treat with intravenous steroids. Administer additional anti-inflammatory measures, as needed.
 - Add prophylactic antibiotics for opportunistic infections in the case of prolonged steroid administration.

- **Diarrhea/Colitis:**

Subjects should be carefully monitored for signs and symptoms of enterocolitis (such as diarrhea, abdominal pain, blood or mucus in stool, with or without fever) and of bowel perforation (such as peritoneal signs and ileus).

- All subjects who experience diarrhea/colitis should be advised to drink liberal quantities of clear fluids. If sufficient oral fluid intake is not feasible, fluid and electrolytes should be substituted via IV infusion. For Grade 2 or higher diarrhea, consider GI consultation and endoscopy to confirm or rule out colitis.
- For **Grade 2 diarrhea/colitis**, administer oral corticosteroids

- For **Grade 3 or 4 diarrhea/colitis**, treat with intravenous steroids followed by high dose oral steroids.

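### Table 4 lets a patient restart after recurrent Grade 2 pneumonitis, whereas 11.1.2 requires a permanent stop

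*Combined protocol and SAP*

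**What the plan says.** Section 11.1.2 (Toxicity) gives the pneumonitis rule in full: withhold at Grade 2, and "permanently discontinue pembrolizumab for Grade 3 or 4 or recurrent Grade 2 pneumonitis". It also notes that fatal cases have occurred.

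Table 4 in section 3.3.1 (Dose Modifications) holds drug for Grade 2 pneumonitis. It restarts when "Toxicity resolves to Grade 0-1" and discontinues on "Toxicity does not resolve within 12 weeks of last dose or inability to reduce corticosteroid to 10 mg or less of prednisone or equivalent", the steroid reduction also being due within 12 weeks. Grade 3-4 has its own line with a permanent stop. Recurrence is not mentioned in the row.

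The Note under Table 4 does deal with recurrence, at a higher grade: "Permanently discontinue for any severe or Grade 3 drug-related AE that recurs or any life-threatening event". For further guidance, section 3.3.1 directs the reader as follows: "See Section 4 for supportive care guidelines, including use of corticosteroids".

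**The concern.** The same event gets different answers depending on which section is open. Suppose a patient has Grade 2 pneumonitis, recovers, restarts, and has a second Grade 2 episode that also resolves in time with steroids tapered. Table 4 allows another dose, while 11.1.2 ends treatment.

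Table 4 is the operative text: 3.3.1 says that drug must be withheld according to it. Section 10.4 presents Section 11 as the description of side effects, which is not where an investigator would look for a dosing rule. At stake is avoidable re-exposure to a toxicity with known fatal cases. Section 10.5 describes these patients as minimally symptomatic and usually just monitored at this stage.

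**Working it through.** **Step 1. Does any other provision require the stop?**

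| Provision | What it covers | Requires a stop for recurrent Grade 2 pneumonitis? |
|---|---|---|
| Table 4, pneumonitis, Grade 2 | Non-resolution or failed steroid taper | No |
| Note under Table 4 | Recurrent severe or Grade 3 events; life-threatening events | No |
| Table 4, footnote c | Persistent Grade 2 events, attached to the row for all other toxicity: "Permanently discontinue study drug for persistent Grade 2 adverse reactions for which treatment with study drug has been held" | No |
| 3.5.1, toxicity criteria | Grade 3 or greater | No |
| 3.5.1, discretion and medical circumstances | Any reason the investigator accepts | Permits it, does not require it |
| 4.1.3, pneumonitis, Grade 2 | Steroids: "treat with systemic corticosteroids. When symptoms improve to Grade 1 or less, steroid taper should be started" | No |
| Table 5 | Grade 2 infusion reaction despite premedication | No, different toxicity |
| 11.1.2 | Recurrent Grade 2 pneumonitis | Yes |

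Part of the background in 1.2 was not available to check.

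**Step 2. Does the silence look deliberate?** Section 11.1.2 contains two recurrence stops. One is general: "Permanently discontinue pembrolizumab for any Grade 3 immune-mediated adverse reaction that recurs and for any life-threatening immune-mediated adverse reaction". The Note under Table 4 carries that one in almost the same terms. The other is for recurrent Grade 2 pneumonitis, and the table lacks it, although the pneumonitis row carries the rest of the rule (hold at Grade 2, stop at Grade 3-4). The table can state a stop for a repeated Grade 2 event, since its infusion reaction row has one. The pattern suggests an omission; no reason is given for a choice.

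**Step 3. Do the cross-references lead to 11.1.2?** Section 3.3.1 points to Section 4, and 4.1.3 points back to 3.3.1. Neither names 11.1.2.

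**Step 4. How many patients could be concerned?** The plan gives no figure of its own, so there is nothing to reproduce.

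- Inputs from 11.1.2, in 1567 pooled patients: Grade 1 0.8%, Grade 2 0.8%, Grade 3 0.4%, total 2.0%.
- The grades add up: 0.8 + 0.8 + 0.4 = 2.0. This suggests that each patient is counted once, presumably at worst grade.
- A patient counted at Grade 3 may have had two Grade 2 episodes first. The group at risk is therefore Grade 2 or higher: 0.8% + 0.4% = 1.2%.
- Expected number at risk: 30 × 0.012 = 0.36; at the accrual ceiling of 32 (Section 8), 32 × 0.012 = 0.384.
- Chance of at least one: 1 − (1 − 0.012)^30 = 0.304; for 32, 1 − (1 − 0.012)^32 = 0.320.

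These figures count patients with any Grade 2 or higher pneumonitis. To be re-dosed against 11.1.2, such a patient must restart, recur at Grade 2, recover, complete the taper, and be treated by someone who does not apply 11.1.2. The documents give no rate for any of these steps.

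**The case against.** The best reply is that the rule is already in the protocol as an instruction. Table 4 allows a restart but does not compel one, and nothing says that it is exhaustive or overrides 11.1.2. A reader who applies both texts stops the drug. A reader might infer that the two sections contradict each other, or that the protocol has no stop for this event. The documents support neither: both texts can be obeyed together, and the stop is written down once.

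There are also practical checks. Patients are examined at every cycle (3.4), the team meets at least monthly to discuss each patient, and the principal investigator reviews each patient's adverse events (7.4.1). A second episode would probably be noticed. But none of these checks says what to do about it, and the text that does is not the one 3.3.1 sends people to.

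Finally, 11.1.2 reads in part as general product information and differs from Table 4 elsewhere. For Grade 3 or 4 hyperthyroidism it offers withholding or stopping, where Table 4 assigns one to each grade. So not every difference is a fault in Table 4. That limits the weight of the point, but here the table is the less cautious of the two, and the rest of the pneumonitis rule was carried over.

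**Conclusion.** The point holds as a minor safety consistency correction. Table 4 makes no exception for recurrent Grade 2 pneumonitis, 11.1.2 requires a permanent stop, and no other provision checked mandates it.

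The size is small and cannot be pinned down. The 0.36 patients and 30.4% (32.0% in 32 patients) rest on the pooled rate applying here and on worst-grade counting. The rate in this trial could be lower, because 2.1.2.9 excludes interstitial lung disease and prior pneumonitis that needed steroids. It could also be higher, since no exposure time is given for the 1567 patients, against up to two years here. A reader might take 30.4% as the chance that someone is wrongly re-dosed. It is not: it is the chance of at least one patient with Grade 2 or higher pneumonitis, and recurrences re-dosed would be fewer.

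Nothing here touches the 4-of-15 rule or the primary analysis in Section 8. The case for correcting it is patient safety, not frequency.

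**What to change.** In the pneumonitis row of Table 4, add: recurrent Grade 2, permanently discontinue. The table then matches 11.1.2, and no other change is needed.

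The cost is one table cell at the next amendment, with no added procedures or patients. The downside is that a rare patient with a second, resolved Grade 2 episode stops earlier than Table 4 alone allows, which 11.1.2 already requires.

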3.3 Drug Administration

Trial treatment should be administered on Day 1 of each cycle after all procedures/assessments have been completed as detailed on the Study Calendar (Section 3.4). Trial treatment may be administered up to 7 days before or after the scheduled Day 1 of each cycle due to administrative reasons.

All trial treatments will be administered on an outpatient basis.

Pembrolizumab 200 mg will be administered as a 30 minute IV infusion every 3 weeks. Every effort should be made to target infusion timing to be as close to 30 minutes as possible.

However, a window of -5 minutes and +10 minutes is permitted (i.e., infusion time is 30 minutes: -5 min/+10 min). Premedication for patients who experience an infusion reaction should be administered 60 minutes (+/- 30 minutes) prior to the infusion.

The Pharmacy Manual contains specific instructions for the preparation of the pembrolizumab infusion fluid and administration of infusion solution. Pembrolizumab is administered through a 0.2 to 5 micron sterile, nonpyrogenic, low-protein binding inline or add-on filter. Do not infuse other medications through the same infusion line.

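### For steroid-treated immune-mediated reactions in the catch-all category, Table 4 and Section 11.1.2 set earliest restart points at least about four weeks apart

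*Combined protocol and SAP*

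**What the plan says.** Three places in the combined protocol and SAP bear on when treatment restarts after an immune-mediated event.

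- **Section 3.3.1, Table 4.** The column headed "Timing for Restarting Treatment" has a single entry for the catch-all row (all other drug-related toxicity, Grade 3 or severe): "Toxicity resolves to Grade 0-1". The same entry serves the Grade 2 pneumonitis, Grade 2-3 colitis, Grade 2 liver-test, Grade 2 renal and Grade 3 hyperthyroidism rows. Steroid dose appears only in the discontinuation column, where one ground for stopping is "inability to reduce corticosteroid to 10 mg or less of prednisone or equivalent per day within 12 weeks". The liver-test row lacks that clause.
- **Section 4.1.3.** For the organ-specific events where it prescribes a taper, improvement to Grade 1 is what starts it: "When symptoms improve to Grade 1 or less, steroid taper should be started and continued over no less than 4 weeks". It has no entry for other immune-mediated reactions and does not say when pembrolizumab restarts.
- **Section 11.1.2.** The bullet on other clinically important immune-mediated reactions says "Upon improvement to Grade 1 or less, initiate corticosteroid taper and continue to taper over at least 1 month", and then "Resume pembrolizumab when the adverse reaction remains at Grade 1 or less following corticosteroid taper".

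Sections 3.3.1 and 4.1.3 refer to each other. Neither mentions 11.1.2, and no sentence says which text prevails.

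**The concern.** The event that opens the restart window in Table 4 is the event that only starts the taper in 11.1.2. For a Grade 3 reaction that is immune-mediated, treated with steroids and not listed by organ, both passages apply to the same patient. Two investigators, each following the protocol, could re-dose that patient several weeks apart.

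This is first a safety and consistency matter, because it concerns re-exposure after immune toxicity. There is a lesser scientific side. Evaluating immune responses in each cohort is a secondary objective, and Section 5.1.1 schedules immunologic sampling every 3 weeks. Whether post-restart samples are taken during or after a steroid course could therefore depend on which section the investigator used.

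**Working it through.** The plan states no figure on this point, so there is none to reproduce. The check is a comparison of passages with calendar arithmetic.

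**Inputs**
- Table 4 restart condition, catch-all row: Grade 0-1 reached (Section 3.3.1).
- Section 11.1.2 restart condition: reaction still at Grade 1 or less after the taper. The taper begins on improvement to Grade 1 or less and lasts at least 1 month.
- Dosing interval, 21 days: "Pembrolizumab 200 mg will be administered as a 30 minute IV infusion every 3 weeks" (Section 3.3).
- Accrual ceiling: 32 patients (Section 8).
- Event and interruption rates: Section 11.1.2.

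**Step 1: gap between restart points.** Let day 0 be the day toxicity first reaches Grade 0-1.
- Table 4: earliest restart is day 0.
- Section 11.1.2: earliest restart is day 0 + 1 month, about day 28 to 31.
- Minimum gap: 28 to 31 days, or 28/21 = 1.33 to 31/21 = 1.48 cycles. A longer taper widens it.

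**Step 2: infusions affected.** Let the first scheduled dosing day on or after day 0 be day d, with d from 0 to 20. Doses fall on d, d + 21, and so on, ignoring the 7-day scheduling window. Count those before the 11.1.2 restart point.
- Restart at day 28: two doses if d is 0 to 6, one if d is 7 to 20.
- Restart at day 31: two doses if d is 0 to 9, one if d is 10 to 20.

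So one or two infusions per event are permitted by Table 4 and not yet by 11.1.2.

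**Step 3: does the 10 mg/day clause close the gap?** It is a 12-week stopping limit. Even read as an implied restart condition, it would allow restart once the dose had fallen to 10 mg, which can be before the taper ends. The gap narrows but does not vanish.

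**Step 4: rows reached.**
- *Direct conflict:* the catch-all row, because the 11.1.2 sentence sits in the bullet on other reactions.
- *Conditional:* the pneumonitis, colitis, hepatic and renal rows. The bullet's second sentence is broader ("For suspected immune-mediated adverse reactions, ensure adequate evaluation to confirm etiology or exclude other causes"), but these events have their own bullets in 11.1.2 and none gives a restart time.
- *Weaker:* hypophysitis, where Table 4 also lets therapy continue during endocrine replacement.
- *Outside:* hypothyroidism and type 1 diabetes/hyperglycemia, which have their own rules, and infusion reaction, which involves no taper.

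**Step 5: how many patients.** This assumes that the rates in 11.1.2 carry over to this trial.
- *Narrow reading:* the listed other reactions each occurred in under 1% of 1,567 patients, except arthritis at 1.6%. For arthritis, 0.016 × 32 = 0.5 patients, before restricting to Grade 3 and steroid-treated cases.
- *Broad reading, restartable grades of the named events:* pneumonitis 0.8% + colitis (0.5% + 1.1%) + hepatitis 0.1% + nephritis 0.2% + hypophysitis (0.3% + 0.3% + 0.1%) + hyperthyroidism 0.1% = 3.5%. Then 0.035 × 32 = 1.1 patients, with the other reactions to be added.
- *Generous comparison:* dosing was interrupted for any adverse reaction in 14% and 21% of patients in the two trials cited. That gives 0.14 × 32 = 4.5 and 0.21 × 32 = 6.7 patients, but only steroid-treated immune events among them would matter here.

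**The case against.** The best case on the other side has four parts.

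1. **The texts are compatible.** Table 4 can be read as a minimum condition, and nothing in it compels restart on the day Grade 0-1 is reached. An investigator who waits for the taper satisfies both. This stands: a reader might infer that the two rules can never both be met, and that is wrong. What remains is that Table 4 on its face permits a dose that 11.1.2 still withholds.

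2. **Dosing decisions are routed to 3.3.1.** Section 3.3.1 says to withhold according to Table 4, and 4.1.3 sends the reader to 3.3.1 for dose modification. Section 10.4 cites Section 11 for the side-effect profile. This suggests which text staff will use, but it does not withdraw the 11.1.2 instruction, which is written as a directive. The note under Table 4 carries the substance of the next sentence in the same bullet (permanent discontinuation for recurrent Grade 3 or life-threatening events) but not the sentence on resuming.

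3. **The scope is narrow.** A reader might infer that the whole restart column of Table 4 is contradicted. The documents do not support that, because the restart sentence belongs to one bullet and the organ-specific bullets are silent on restart. The missing steroid clause in the AST/ALT/bilirubin row is likewise an omission of detail: the hepatitis bullet states no restart time for it to contradict.

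4. **The consequences are easily overstated.** It is tempting to say that Table 4 would re-dose patients on near-full steroid doses. The documents give no taper doses, so that is inference. Section 4.1.2 exempts steroids given for suspected immunologic events from its prohibition, so it does not settle the matter either way. Confounding of the calcitonin, imaging or immune endpoints is possible, but nothing in the documents allows it to be sized.

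**Conclusion.** The inconsistency is real and limited. For steroid-treated other immune-mediated reactions at Grade 3 or severe, the earliest permitted restart in Table 4 and in Section 11.1.2 differs by at least about 28 to 31 days, or one to two infusions per event. This rests on the ordinary reading that resuming after the taper means after it is completed, and on the 21-day dosing interval.

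Extension to the pneumonitis, colitis, hepatic and renal rows depends on reading the 11.1.2 bullet as general, which its second sentence suggests but does not establish. If the 11.1.2 rates apply here, about one patient of 32 would have a restartable event among the named reactions even on that broad reading, with the other reactions adding to it. No effect on the primary analysis (4 or more of 15 per cohort) is shown. It merits correction because it concerns re-dosing after immune toxicity, and correction needs only wording.

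**What to change.** Reconcile Section 3.3.1 Table 4, Section 4.1.3 and Section 11.1.2 so that one restart condition applies throughout. The text should state:

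- whether steroid-taper status is part of the restart condition, in addition to grade; and
- which reactions the condition covers: only the catch-all category, or the organ-specific rows as well.

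Which condition applies and which section prevails are for the sponsor and manufacturer to decide. The wording need not be identical in all three places; a cross-reference to a single statement would do. While editing, the sponsor may also wish to settle whether the AST/ALT/bilirubin row is meant to carry a steroid clause.

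The cost is a wording amendment. Some patients would restart earlier or later than one of the present texts implies. Sample size, endpoints and analysis are unchanged.
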